7.6.2.2 Doses administered

Population SP

Compliance will be calculated according to the formula: cumulative dose received (in mg) / protocol dose (in mg)

The theoretical protocol dose being equal to 10 mg x treatment duration (in days).

It will be described according to the usual descriptive statistics.

7.6.2.1 Modified dosage and temporary discontinuation

Population SP

The number of patients who had at least one dosage change and the number of patients who had at least one temporary stop or deferral will be described according to standard descriptive statistics.

7.6.2.2 Permanent cessation of treatment

Population SP

The number and percentage of patients permanently discontinuing protocol treatment and the reasons for discontinuing protocol treatment (% of the number of patients discontinuing treatment) will be described according to standard descriptive statistics. .

7.6.2.1 Other criteria

Population SP

The time from the end of 1^{ère} (chemo)embolization to the resumption of everolimus treatment will be calculated in days and described according to standard descriptive statistics.

Similarly, the time between the end of the 2^{ème} (chemo)embolization and the resumption of everolimus treatment will be calculated and presented.

7.6.3 ISG

The summary of the SAEs will be provided by pharmacovigilance.

7.6.4 Toxicities

Population SP

Toxicities (graded according to NCI-CTC v 4.0) will be described by:

- The total number of patients by maximum grade of toxicity (grade 1-2-3-4-5);
- The number of patients and the maximum toxicity grade achieved (grade 1-2-3-4-5) by SOC and type of toxicity;
- Total number of patients by maximum grade of toxicity by grouping grades (grade 1-2 and grade 3-4-5);
- The number of patients and the maximum grade of toxicities achieved by grouping the grades (grade 1-2 and grade 3-4-5) by SOC and type of toxicities.

7.6.5 WHO

Population SP

The evolution of the WHO performance index during treatment will be described by cross-tabulating the WHO index at inclusion with the WHO index of the last available on-treatment assessment.

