Number of subjects needed	72 patients
Planned study period	
Expected start date of inclusion: November 2012
 
Expected completion date of inclusion: April 2016
 
Primary endpoint analysis: April 2018
 
End of study: January 2019

EXAMINATION AND FOLLOW-UP SCHEDULE

	BEFORE TREATMENT	DURING EMBOLIZATION OR CHEMOEMBOLIZATION		DURING TREATMENT WITH EVEROLIMUS (24 months maximum)	AFTER STOPPING TREATMENT WITH EVEROLIMUS (after 24 months)
	Within 4 weeks prior to inclusion	Within 7 days prior to each embolization or chemoembolization	After embolization or chemoembolization	Every 3 months +/- 1 week	Every 3 months +/- 1 week
Informed consent	X				
CLINICAL EXAMINATION					
Weight, general condition WHO	X	X		X	X
Functional symptoms related to hormonal hypersecretion	X				
Medical and surgical history and treatments related to the endocrine tumor	X				
MORPHOLOGICAL EXAMINATION					
Triphasic thoracoabdomino-pelvic CT (to be performed in the investigating center, without injection, arterial time, portal time) *with measurement of liver metastases according to RECIST v1.1 criteria	X*		X**	X*	X***
ECG ± cardiological opinion if necessary	X				
BIOLOGICAL ASSESSMENT					
CBC/platelets, total and conjugated bilirubin, AST, ALT, PAL, creatinine, 24-hour proteinuria if treated with streptozotocin	X	X		X	
INR, TCA	X	X		X	
albumin, urea, blood ionogram, GGT	X			X	
Serum cholesterol and triglycerides, fasting blood glucose and HbA1c	X			X	
Chromogranin A, urinary 5HIAA	X			X	
B viral serology (HBV-DNA, HBsAg, anti-HBsAb, anti-HBcAb) and C****	X			****	
Pregnancy test for women of childbearing age	X (within 7 days of starting treatment)				

*With target measurement according to RECIST v1.1 criteria

**To be performed for technical reasons only. Measurements should not be used for evaluation of tumor response

*** If everolimus is discontinued for reasons other than hepatic progression, continue morphological monitoring until hepatic progression occurs

**** In case of B and C viral serology, follow up the DNA and RNA load respectively every 3 to 6 weeks (see table 2-2 and 2-3)

I. OBJECTIVES OF THE TRIAL

1. Main objective

The primary objective of the study is to determine whether treatment with everolimus for 24 months prolongs progression-free survival according to RECIST 1.1 criteria. The primary endpoint will be progression-free survival at 24 months in patients receiving hepatic embolization or chemoembolization followed by everolimus therapy.

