- Clinical assessment: weight, general condition (WHO)
- Evaluation of the tolerance of the previous embolization or chemoembolization
- Biological check-up:
 - CBC-platelets
 - INR, aPTT, creatinine, bilirubin (total, conjugated), AST, ALT, PAL

NB: An abdominal CT scan may be performed if necessary for technical reasons before the 2nd embolization or chemoembolization session. Caution: this imaging should not be used to evaluate the response to treatment of metastases.

Every 3 months (+/- 1 week) from the date of the first embolization or chemoembolization (except DNA and ARC monitoring for positive serology)

- Clinical assessment: WHO, weight, evaluation of side effects
- Bioassay:
 - CBC/platelets, urea and creatinine + calculated creatinine clearance (Cockcroft formula), blood ionogram
 - INR, aPTT, albumin, alkaline phosphatase, AST, ALT, bilirubin (total and conjugated), gamma-GT
 - Serum cholesterol and triglycerides
 - Fasting blood glucose and HbA1c
 - Chromogranin A, urinary 5HIAA
- If HBV positive, monitor DNA approximately every 3 weeks or 6 weeks depending on the result (see Table 2-2)

- If HCV positive, monitor RNA every 6 weeks (see Table 2.3)
- Morphological assessment: triphasic thoracic-abdominal-pelvic CT scan with target measurement according to RECIST V1.1 criteria (Appendix 3). Evaluation CT scans should be performed in the same center as the initial examination

NOTE: Patients whose treatment is temporarily or permanently discontinued due to an adverse event or laboratory abnormality suspected to be related to everolimus should be monitored at least weekly until the adverse event resolves or returns to Grade 1

2. Post-treatment monitoring protocol

- **After discontinuation of treatment for hepatic progression**
 - After hepatic progression, the clinical, biological and morphological monitoring of the patient will be left to the investigator's discretion
- **After discontinuation of treatment for a reason other than hepatic progression**
(e.g. toxicity, extra-hepatic progression, patient's wish, :)
 - Morphological surveillance: CT every 3 months until liver progression occurs, according to the same modalities as the initial morphological evaluation (triphasic thoraco-abdomino-pelvic CT with target measurement according to RECIST V1.1 annex 3)

IX. STOP PROCESSING THE STUDY

The processing of the study will be stopped in case of:

- Investigator's decision

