Overall survival will be defined as the time interval between the date of inclusion and the date of death regardless of the cause of death or the date of last news for living patients.

Tolerance to treatment will be assessed by:

- duration of treatment, doses received, dose reductions and deferrals
- Toxicities collected at each monthly visit, and described according to NCI-CTC version 4.0 criteria; Grade 3, Grade 4 and Grade 5 toxicities will be reviewed.
- the number and description of SAEs
- the evolution of the WHO performance index.

Calculation of the number of subjects needed

According to the literature, the median progression-free survival after embolization or chemoembolization ranges from 15 to 19 months with a progression-free survival rate of approximately 35%. As there is no information on progression-free survival in the literature, the hypotheses were built on the progression-free survival data.

The assumptions used to calculate the number of subjects are as follows:

H0: a 24-month progression-free survival rate of less than 35% is not acceptable

H1: A 24-month liver progression-free survival rate greater than 35% would demonstrate the utility of everolimus therapy with an expected 24-month liver progression-free survival rate of 50%,

To obtain a power of 80% with a first-species risk of 5% (one-sided), it is required to include 68 patients according to the assumptions established above (using the exact binomial distribution).

Taking into account a rate of lost to follow-up or patients not evaluable for any reason except death, 72 patients will be included.

3. Statistical analysis plan

Populations of analysis

Patients included in the study will be described (ITT) as well as patients not evaluable for the primary endpoint.

A patient is considered evaluable if he or she has received at least one dose of everolimus and one evaluation.

All efficacy analyses will be performed on a modified intention-to-treat basis (evaluable patients) included in the study regardless of eligibility criteria and treatment received.

Tolerability population: the ITT population that received at least one dose of the treatments.

In all cases of discontinuation, the patient remains in the intention-to-treat analysis. There is no exclusion period for a subsequent therapeutic trial.

Main analyses

A statistical analysis plan will be written prior to freezing the database.

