6.1.2 Population for tolerance analysis (SP)

It is defined as the ITT population that received at least one dose of everolimus. The safety criteria will be evaluated in this population.

A listing of patients excluded from the PP population will be provided with the reasons for exclusion.

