7.1.7 Statistics

Quantitative variables will be described using the number, median, mean, standard deviation of the mean, minimum, maximum, and interquartile range (Q1-Q3). Quantitative variables may be categorized using their median or a cut-off known from the medical literature.

Categorical variables will be described using percentages, and if necessary their two-sided 95% confidence intervals (calculated using the exact method).

Missing values will not be included in the calculation of frequencies and percentages.

The **confidence intervals** provided will be two-sided 95% confidence intervals, except for the primary criterion where a one-sided 95% confidence interval will be given.

Survival data will be estimated and plotted using the Kaplan-Meier method (Kaplan and Meier, 1958).

This will be described by the median and rates calculated at different times. Two-sided 95% confidence intervals will be provided. Confidence intervals for the rates will be constructed from the Greenwood variance calculated using the log-log transformation.

The median follow-up time will be calculated using the reverse Kaplan-Meier method (Shemper, 1996).

For uni and multivariate analyses, hazard ratios will be estimated using a Cox model (Cox, 1984). The proportionality of the rates will be tested using the graphical representation and the test based on Schöenfeld residuals (Grambsch, 1994); the linearity of the effect of the continuous variables on the risk will be assessed from the graphical representation of the martingale residuals. Confidence intervals for the coefficient estimates of the Cox models will be calculated using the Wald method.

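### The WHO performance-status table in SAP 7.6.5 can understate deterioration, because it keeps only the last on-treatment value and has no row for death or for no assessment

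*SAP*

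**What the plan says.** Protocol XII.2 (Secondary criteria) names "the evolution of the WHO performance index" as one of four components of tolerance. The SAP lists it under Other criteria in section 5.7 and places its analysis within section 7.6, on tolerance.

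SAP 7.6.5 reduces it to a single table, made by "cross-tabulating the WHO index at inclusion with the WHO index of the last available on-treatment assessment". The population is SP, of which the SAP says "It is defined as the ITT population that received at least one dose of everolimus". The SAP does not define on-treatment for this purpose, and it gives the table no category for death, for treatment stop or for no value.

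SAP 7.1.5 replaces no missing data except where specified, and nothing is specified for WHO. SAP 7.1.7 adds: "Missing values will not be included in the calculation of frequencies and percentages".

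Protocol VIII.1 schedules WHO within 7 days before each (chemo)embolization session and then "Every 3 months (+/- 1 week) from the date of the first embolization or chemoembolization", where the visit content is "Clinical assessment: WHO, weight, evaluation of side effects". No end-of-treatment WHO assessment is defined.

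Two places in the protocol do not agree with this schedule:
- XII.2 speaks of "Toxicities collected at each monthly visit", but no monthly visit appears in the schedule or in VIII.1.
- The schedule row "Weight, general condition WHO" is also marked in the column for after everolimus has stopped. VIII.2 lists only CT after a stop for a reason other than hepatic progression, and leaves monitoring to the investigator after hepatic progression.

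**The concern.** A last-value table suits a measure that is recorded up to the moment of stopping. Here WHO is scheduled at wide intervals, and the patients most likely to lack a late value are those who stop early or die. Their decline is then replaced by an earlier and better value, or they leave the denominator.

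The choice also differs from the neighbouring analysis. SAP 7.6.4 summarises toxicity by maximum grade per patient, so a severe event that resolves still counts. Under 7.6.5 a WHO decline that resolves leaves no trace, although the section sets out to describe how WHO changes during treatment.

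At stake is how one descriptive tolerance table is read. A reader could take a low proportion worsened as a finding about the patients when part of it comes from the rule.

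**Working it through.** The plan states no figure for WHO change, so there is nothing to reproduce. The check follows each kind of patient through the rule and then sizes the effect under stated assumptions.

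**Step 1. What the table shows for each kind of SP patient**

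| Course | Shown under SAP 7.6.5 |
|---|---|
| Declines, and this is the last recorded on-treatment value | Worsened (correct) |
| Declines at one visit, recovers by the last one | Not worsened |
| Declines after the last assessment and stops everolimus | Earlier status |
| Dies after the last assessment | Last living status |
| No on-treatment value | Left out of percentages |

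The number shown as worsened can only be too low, because the worst value is never better than the last. For omitted patients, the percentage is too low only if they did worse than those retained.

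**Step 2. Can these cases arise under the protocol?**

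With 3-monthly visits, the last value precedes a stop by up to about 3 months. If stops fall evenly between visits, the mean gap is 3/2 = 1.5 months. If WHO were instead recorded at the monthly visits mentioned in XII.2, the gap would be at most about 1 month, with a mean of 1/2 = 0.5 months. Protocol Tables 1-1 and 1-2 end everolimus when toxicity requires an interruption of 3 weeks or more. Onset, interruption and permanent stop can thus all fall between two 3-monthly assessments.

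A patient planned for one session who stops before the month-3 visit has no scheduled WHO value after the first dose. A patient who reaches a second session has one, taken in the 7 days before it.

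**Step 3. Illustrative size (all rates assumed)**

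Take the largest possible SP population, 72 patients (SAP 5.5). Suppose 5%, 10% or 20% stop or die between visits with an unrecorded decline, and 20% of the others are worse at their last value. Counts are rounded.

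| Unrecorded declines | Others worsened | Shown, earlier status kept | Shown, patients dropped | All declines counted |
|---|---|---|---|---|
| 4 (5%) | 14 of 68 | 14/72 = 19.4% | 14/68 = 20.6% | (14+4)/72 = 25.0% |
| 7 (10%) | 13 of 65 | 13/72 = 18.1% | 13/65 = 20.0% | (13+7)/72 = 27.8% |
| 14 (20%) | 12 of 58 | 12/72 = 16.7% | 12/58 = 20.7% | (12+14)/72 = 36.1% |

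The smallest gap is 25.0 − 20.6 = 4.4 points and the largest is 36.1 − 16.7 = 19.4 points. With no unrecorded declines the gap is zero. If the 4 dropped patients had not in fact worsened, the table would be slightly too high (14/68 = 20.6% against 14/72 = 19.4%).

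**The case against.** The strongest reply is that the rule matches its stated scope. It describes WHO during treatment, and the tolerance objective is likewise limited to the treatment period. The choice between last and worst value is partly preference, and any table of two time points hides what happens between them. Other analyses report the same patients: permanent stops with reasons (7.6.2), serious adverse events (7.6.3), maximum toxicity grade including grade 5 (7.6.4) and overall survival (7.5.4). The word available may also admit an unscheduled assessment or one at the visit where treatment is stopped. Protocol VIII.1 asks for at least weekly monitoring after a stop for suspected everolimus toxicity, although it does not name WHO there.

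Much of this stands. A reader might infer that the trial's tolerance results as a whole will look better than they are. The documents do not support that: WHO is one descriptive component with no test or threshold, and the other summaries record stops and toxic deaths directly. A reader might also infer that the gap is necessarily 3 months, but the reference to monthly visits leaves this unsettled.

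The other summaries do not correct the WHO table itself, however. It will be read as the result for its own component. SP has a known total, so a shortfall could be noticed, but the table would not say who is missing or why.

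**Conclusion.** The point holds for the WHO table and no further. As specified, the table can understate deterioration in three ways: worsening that recovers, decline or death after the last assessment, and omission of SP patients with no on-treatment value.

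The size cannot be derived from the documents. The range of about 4 to 19 points rests on assumed shares of 5% to 20% and on every affected patient having worsened. It shows what is possible and is not an estimate. The true effect may be zero.

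This is a minor reporting matter. It does not touch the 24-month primary endpoint, its decision rule or any other efficacy result.

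**What to change.** In SAP 7.6.5:
- Cross-tabulate WHO at inclusion against the worst on-treatment value from first everolimus dose to treatment stop, and state which assessments count as on-treatment.
- Add rows for died on treatment and for no on-treatment assessment.
- Use the whole SP population as denominator, as an explicit exception to 7.1.7.
- Keep the last-value table alongside.

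The cost is one revised table, built from WHO values, treatment dates and death dates already collected. It has to be settled before the database freeze (SAP 7.1.2).

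There are two limits. The worst value will include brief, reversible changes and decline due to progression, which a single-arm trial cannot separate from intolerance. The main table will also still miss an unrecorded decline in a patient who stops alive between visits.

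Post-stop WHO values could help with that last group, but only as a supplement, because they mix in later progression and later therapy. Before they are used, the schedule, which marks WHO after stopping, must be reconciled with protocol VIII.2, which does not list it. The monthly visit in XII.2 must likewise be reconciled with the 3-monthly schedule.

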7.7 Evaluations of exploratory analyses

- An analysis of predictive factors for overall survival and progression-free survival will be performed using univariate and multivariate Cox models. The predictive factors studied will be the parameters identified at inclusion:
 - Previous treatment (yes vs. no)
 - WHO (0 vs 1-2)
 - Age (< vs. \geq median)
 - Gender (Male vs Female)
 - Presence of carcinoid heart disease (yes vs. no)
 - Tumor grade (G1 vs G2)
 - Tumor site (appendix vs. jejunum/ileum vs. colon/rectum vs. other)
 - Bilateral liver metastases (yes vs. no)
 - Extrahepatic metastases (yes vs no)
 - BMI (< 25 vs \geq 25)
 - Chromogranin A ($>2N$ vs $<2N$ with N=200 ng/mL)
 - Decrease from Chromogranin A inclusion at M3 (2 thresholds will be tested: $>50\%$ vs $\leq50\%$ and $>30\%$ vs $\leq30\%$)
 - Decrease from baseline in urinary 5HIAA at M3 (2 thresholds will be tested: $>50\%$ vs $\leq50\%$ and $>30\%$ vs $\leq30\%$)
- As an exploratory measure, progression-free survival between embolization alone and chemoembolization will be compared by a logrank test (if the number of patients in each group is sufficient).

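### SAP 7.7 splits every quantitative predictor into two groups and tests each month-3 marker fall at two cut-offs, which can lose power and raises the false-positive rate in the exploratory analyses

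*SAP*

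**What the plan says.** SAP 7.7 states: "An analysis of predictive factors for overall survival and progression-free survival will be performed using univariate and multivariate Cox models". Five of the thirteen listed factors are quantitative, and all five are cut in two:

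- age, as "Age (< vs. \geq median";
- BMI, at 25;
- inclusion chromogranin A, as "Chromogranin A ($>2N$ vs $<2N$ with N=200 ng/mL", a cut at 400 ng/mL;
- the month-3 fall in chromogranin A, as "Decrease from Chromogranin A inclusion at M3 (2 thresholds will be tested: $>50\%$ vs $\leq50\%$ and $>30\%$ vs $\leq30" per cent;
- the month-3 fall in urinary 5HIAA, with the same pair of cut-offs: "Decrease from baseline in urinary 5HIAA at M3 (2 thresholds will be tested: $>50\%$ vs $\leq50\%$ and $>30\%$ vs $\leq30" per cent.

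The underlying values are collected as numbers. SAP 7.2.2 to 7.2.4 describe age in years, BMI in kg/m², chromogranin A in ng/mL and urinary 5HIAA in mg/24h, and protocol section VIII.1 repeats both markers every three months.

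The general methods in SAP 7.1.7 permit splitting without requiring it: "Quantitative variables may be categorized using their median or a cut-off known from the medical literature". The same section says that "the linearity of the effect of the continuous variables on the risk will be assessed from the graphical representation of the martingale residuals". SAP 7.7 gives no source for its cut-offs, no multiplicity correction, and no rule for which of the two marker thresholds is reported as the result or enters the multivariate model. The protocol (XII.3) and the SAP (3.2.3 and 7.7) label these analyses exploratory.

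**The concern.** A factor search in 72 patients has few events to work with. Reducing a measured value to high or low discards part of the information in it, so a real gradient is more likely to be missed, and patients just either side of a cut are treated as different. Continuous coding is available at no cost in data, and the linearity check that it needs is already planned. As SAP 7.7 stands, no continuous covariate is left for that check.

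Testing one marker change at two thresholds gives two chances of a nominally significant result. Without a stated rule, the more favourable threshold can become the reported finding.

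At stake is how far any predictive factor found in this trial can be trusted. The point concerns only the scale on which predictors enter the models.

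**Working it through.** **The plan's own figure.** The documents state no power, effect size, event count or test level for SAP 7.7. The only design figure is the primary one (SAP 5.5 and 5.6.1), and it reproduces: P(X ≥ 31 | n = 68, p = 0.35) = 4.61%, P(X ≥ 31 | n = 68, p = 0.50) = 80.2%, and 68/0.95 = 71.6, rounded up to 72.

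**Inputs for the power check**

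- From the SAP: 72 patients; 50% event-free at 24 months (the H1 rate); point date 1 September 2017, set 24 months after the last inclusion.
- From the protocol: inclusions expected to start in November 2012.
- Assumed: exponential event times, normal predictor, log-linear effect, hazard ratio (HR) per SD of 1.3 to 1.6, two-sided 5%.

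**Events.** With follow-up cut at 24 months: 72 × 0.50 = 36. With follow-up to the point date and even accrual over 34 months: λ = ln 2/24 = 0.0289 per month, mean event-free share = 0.5 × (1 − e^(−34λ))/(34λ) = 0.318, events = 72 × 0.682 = 49.

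**Power.** For D events, continuous coding gives Φ(√D × ln HR − 1.96). A split with share p in one group multiplies the information by r = φ(z_p)²/[p(1 − p)]:

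- 50/50: r = 0.637 (equal to 2/π)
- 30/70: r = 0.576
- 20/80: r = 0.490

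At 36 events a median split is worth 0.637 × 36 ≈ 23 events.

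Example with D = 36 and HR 1.5: 6 × 0.4055 = 2.433. Continuous: Φ(0.473) = 68.2%. Median split: 2.433 × √0.637 = 1.941, so Φ(−0.019) = 49.2%.

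| Events | HR per SD | Continuous | Median split | Loss (points) |
|---|---|---|---|---|
| 36 | 1.3 | 35.0% | 24.1% | 10.9 |
| 36 | 1.4 | 52.3% | 36.3% | 16.0 |
| 36 | 1.5 | 68.2% | 49.2% | 18.9 |
| 36 | 1.6 | 80.5% | 61.4% | 19.1 |
| 49 | 1.3 | 45.1% | 31.0% | 14.0 |
| 49 | 1.4 | 65.4% | 46.8% | 18.6 |
| 49 | 1.5 | 81.0% | 62.0% | 19.0 |
| 49 | 1.6 | 90.8% | 74.7% | 16.1 |

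Losses are taken before rounding. Simulated Cox score tests (72 patients, 4,000 runs per setting) agree to within a few points: 11 to 22 points for a median split over both event counts, and 9.3 to 20.9 in a separate run at about 36 events with 50/50 and 30/70 splits.

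**Outside that range.** At 36 events a median split costs 5.5 points at HR 1.2 and 7.3 at HR 2.0. At HR 1.6 and 36 events, a 30/70 split costs 23.4 points and a 20/80 split 30.0. Over 34 to 60 events, HR 1.2 to 2.0 and splits from 50/50 to 20/80, the loss runs from about 1 to 30 points.

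**Two cut-offs.** A fall above 50% is also a fall above 30%, so the two splits are nested. If shares p30 and p50 exceed each cut, the two test statistics correlate under the null at √[p50(1 − p30)/(p30(1 − p50))]. The chance that at least one passes ±1.96 is then:

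| p30 | p50 | Correlation | False-positive rate |
|---|---|---|---|
| 0.60 | 0.50 | 0.82 | 7.7% |
| 0.50 | 0.30 | 0.65 | 8.5% |
| 0.60 | 0.20 | 0.41 | 9.3% |

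Two independent tests would give 1 − 0.95² = 9.75%. For both markers together, taken as independent of each other, the rate is 1 − (1 − 0.077)² = 14.8% to 1 − (1 − 0.093)² = 17.7%, against 9.75% with one test per marker.

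**The case against.** **On size.** The 2/π figure belongs to a normal variable cut at its median, and only age is cut there. The shares either side of BMI 25, 2N, 30% and 50% are unknown, and nothing shows that the marker changes are normal or act log-linearly. The 50% rate is the expected liver progression-free rate, while progression-free survival in SAP 5.7.2.3 also counts extrahepatic progression, so its events should be at least as many. No overall survival calculation is possible from the documents. All of this stands. The power figures are therefore illustrations, although at 60 events a median split still costs 12.6 to 19.3 points over the same hazard ratios.

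**On the plan's safeguards.** The cut-offs are fixed in advance, so there is no open search for the best cut. SAP 7.1.7 allows median or literature cuts, and support for 25 or 2N may exist in sources that the SAP does not cite. This also stands, but a pre-specified cut still discards information, and two pre-specified cuts still give two tests.

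**On weight.** The analyses are exploratory. With thirteen factors, the double thresholds make fifteen comparisons per endpoint. If these were independent 5% tests, the chance of any false positive would fall only from 53.7% to 48.7% on dropping two. The gain is in the interpretability of the two marker results.

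**On the remedy.** SAP 7.1.4 keeps confirmed outliers unmodified, which exposes continuous terms to extreme values. A log scale for the markers limits this. A transformation chosen after viewing residuals is data-driven and must be labelled so.

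**Stronger readings that the documents do not support.** A reader might infer a fixed power cost for every predictor, but no document gives the inputs for one. A reader might say that a median age cut cannot be reproduced elsewhere, but SAP 7.1.7 has medians reported, so another series could apply the same value. A reader might see SAP 7.1.7 and 7.7 as contradictory, but the linearity check is a general statement that 7.7 leaves idle.

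**Conclusion.** The point holds as a minor improvement to the exploratory analyses. SAP 7.7 splits all five quantitative predictors and tests each month-3 fall twice with no rule for which test counts.

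The power cost is conditional: roughly 10 to 20 points for a near-central split, under the assumptions listed in the check, none of which the documents supply. It shrinks when effects are weak or very strong, or when events are few; it grows with unbalanced splits; and it vanishes if risk really steps at the chosen cut. The false-positive rise, from 5% to about 8 to 9% per marker, depends only on the shares exceeding each threshold and is modest because the splits are nested.

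A reader might infer that the trial's main conclusion is at risk. It is not: the 31-of-68 rule uses none of these models.

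**What to change.** In SAP 7.7, before the database is frozen (the limit set in SAP 7.1.2):

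- enter age and BMI as continuous linear terms, for example per 10 years and per 5 kg/m²;
- enter inclusion chromogranin A as log(value);
- enter each month-3 change as one continuous term, log(month-3 value / inclusion value), with one test per marker;
- check linearity with the martingale residuals already planned in SAP 7.1.7, and label any transformation chosen after that check as data-driven;
- keep the listed cuts (median age, BMI 25, 2N, 30%, 50%) only to display Kaplan-Meier curves, without separate tests.

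The cost is SAP wording. No new data, patients or procedures are needed, and each predictor still uses one degree of freedom. The downside is that hazard ratios are then per unit or per doubling, which is less simple to read than high versus low, and that a transformation may be needed if the residual plot shows a clear curve or step.
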